7.3.2 Follow-up for Adverse Events

The occurrence of an adverse event (AE) or serious adverse event (SAE) may come to the attention of study personnel during interactions between care coordinators and study participants and their proxies. The occurrence of an AE or SAE may also come to the attention of study personnel upon review of medical records.

All AEs will be captured on the appropriate case report form (CRF). Information to be collected includes event description, time of onset, qualified medical professional’s assessment of severity, relationship to study, and time of resolution/stabilization of the event. All AEs occurring while on study must be documented appropriately regardless of relationship. All AEs will be followed to adequate resolution.

Changes in the severity of an AE will be documented to allow an assessment of the duration of the event at each level of severity to be performed.

Reporting schedule:

- All **adverse events that are serious (SAE) and unexpected** (i.e., have not been previously reported for the study’s intervention) will be reported to the IMPACT Collaboratory Regulatory and Data Team and NIA IMPACT Collaboratory PO for dissemination to the IMPACT Collaboratory DSMB Chair (or the project’s Safety Officer) within 48 hours of the study’s knowledge of SAE.
 - Only those adverse events that are serious (SAE), unexpected, **and related to the intervention** must also be reported to Advarra IRB. Unexpected and **unrelated** SAEs will be reported to Advarra IRB on a case-by-case basis if requested by the IMPACT Collaboratory DSMB Chair (or the project’s Safety Officer) or NIA IMPACT Collaboratory PO.
- All unexpected deaths will be reported to IMPACT Collaboratory Regulatory and Data Team and NIA IMPACT Collaboratory PO for dissemination to the IMPACT Collaboratory DSMB Chair (or the project’s Safety Officer) within 24 hours of study’s knowledge of death.

- Advarra IRB does not require the specific reporting of death outside of the SAE reporting requirement above, but they will be notified on a case-by-case basis if requested by the IMPACT Collaboratory Chair (or the project's Safety Officer) or NIA IMPACT Collaboratory PO.
- All **unanticipated problems (UPs)** will be reported to the IMPACT Collaboratory Regulatory and Data Team and NIA IMPACT Collaboratory PO for dissemination to the Advarra IRB and the IMPACT Collaboratory DSMB Chair (or the project's Safety Officer) within 48 hours of the study's knowledge of the event.
- The summaries of all previously reported unexpected and related SAEs, deaths, and UPs, *as well as* all other SAEs and AEs will be reported to IMPACT Collaboratory Regulatory and Data Team for dissemination to Advarra IRB, NIA IMPACT Collaboratory PO, and the IMPACT Collaboratory DSMB Chair (or the project's Safety Officer) 6 months after the start of enrollment and at the end of enrollment or data collection (whichever comes later), or at a frequency requested by the IMPACT Collaboratory DSMB Chair (or the project's Safety Officer) or NIA IMPACT Collaboratory PO.

7.4 Safety Monitoring

The NIA Guidelines on Data and Safety Monitoring generally require that a NIA-appointed Data and Safety Monitoring Board or Safety Officer monitor clinical trials. This trial will have oversight from the Data and Safety Monitoring Board appointed by the NIA IMPACT Collaboratory.

8 INTERVENTION DISCONTINUATION

No interim analysis is planned, as the planned trial is fairly short, with 12 months of follow-up for the combined outcome of an emergency department visit or hospital admission. Interim analyses of emergency department visits and hospital admissions will not likely be sufficiently powered to be meaningful.

However, findings that might trigger a safety review are the number of unexpected deaths in the trial. Such findings are presented to the study statistician or to the Data and Safety Monitoring Board (DSMB) statistician to review the events by group to determine whether there are statistical as well as clinical concerns. The statistician reports his findings to a closed session of the DSMB or to the Safety Officer and/or NIA. The findings are used to determine what steps will be taken.

9 STATISTICAL CONSIDERATIONS

9.1 General Design Issues

The trial is based on the hypothesis that assigning care coordinators to PLWD whose care partners' perceive a problem with care coordination will result in fewer ED visits and hospitalizations than assigning care coordinators to PLWD at the time of hospital

discharge. To avoid circularity, we will separate exposures and outcomes in time. That is, we will have a 3-month exposure period, during which a hospitalization that prompts care coordination will only be counted for the exposure and not as an outcome.

The 3-month time period was chosen, based on preliminary data suggesting that more fragmented care over 12 months independently increases the risk of an incident ED visit^(under review) or incident hospital admission²¹ in the subsequent 1-3 months, compared to less fragmented care.

A parallel design was chosen because it is a robust design that allows for concurrent comparisons. The outcome of ED visit or hospitalization will be measured using Medicare claims data, which are the gold standard, because they capture events across health systems and are thus broader than EHRs.

9.2 Sample Size and Randomization

The primary outcome is the number of events (emergency department visits or hospitalizations) / person-time alive. Preliminary data (for the control group) show an average event rate per person of 1.99 events over 334 live days (0.92 years). Using Poisson regression, with a sample size of 688 PLWD and assuming 20% attrition and $\alpha = 0.05$, we have >90% power to find an event rate ratio of 0.74 (i.e., a reduced event rate of 1.47 or lower in the intervention group vs. 1.99 in the control group), which is a meaningful difference. Data will be analyzed using an intention-to-treat approach. We will use descriptive statistics to report our secondary implementation outcomes; these are designed to inform future iterations and dissemination of this intervention, rather than test hypotheses per se.

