This study is based on a conceptual model that has arisen from [name] previous work (Figure 2).⁴ The model describes the relationships among fragmentation, communication, and harm and identifies different time points at which interventions could occur. The intervention we are proposing in this application would detect and address gaps in communication before they cause harm (Box F). By contrast, usual care would intervene after a hospital admission (Box G). This is not to say that all hospital admissions are preventable or related to fragmented care; they are not. However, our preliminary data suggest that more fragmented care for Medicare beneficiaries over 12 months independently increases the risk of an incident ED visit^(under review) or incident hospital admission²¹ in the subsequent 1-3 months, compared to less fragmented care. The magnitude of this association is a 31% increase in the risk of an ED visit (95% confidence interval [CI] 29%, 34%) and, separately, an 18% increase in the risk of a hospital admission (95% CI 12%, 24%). If this risk can be modified with better communication, the potential for averted ED visits and hospital admissions is substantial.

Figure 2. Conceptual model describing the relationships among fragmentation, communication, and harm

Of note, in a nationwide survey, Black Medicare beneficiaries were significantly more likely than White Medicare beneficiaries to report experiencing an adverse event that they thought could have been prevented with better communication among their healthcare providers.²² Addressing concerns about care coordination has the potential to avert preventable events that may disproportionately affect racial minorities.

3 **STUDY DESIGN**

We will conduct a pragmatic clinical trial embedded in an ACO (ePCT) with prospective randomization. The trial consists of a parallel design with two groups of equal size. Masking is not feasible.

The trial will determine the comparative effectiveness of two different approaches for allocating care coordinators to PLWD. The primary outcome is the combined outcome of ED visit or hospitalization over 12 months of follow-up. The secondary outcome consists of implementation measures (acceptability, appropriateness, fidelity, and efficiency), which will be used to inform future dissemination.

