The setting for the study is the NewYork Quality Care (NYQC) ACO, the ACO that brings together NewYork-Presbyterian Hospital, Weill Cornell Medicine, and ColumbiaDoctors.^{23,24} Individuals in the study have already been assigned to NYQC by Medicare and will be contacted by care coordinators who already work with NYQC. Interactions between care coordinators and individuals in the study (PLWD or their proxies) will be done by telephone or by video, both of which are part of standard care.

The study population will consist of Medicare beneficiaries ≥ 65 years old who: 1) are attributed to NYQC by Medicare, 2) have dementia (using the previously validated Bynum-Standard 1-year definition for ICD-10 codes),^{25,26} 3) reside in the community, and 4) had fragmented ambulatory care in the previous 12 months (defined as a reversed Bice-Boxerman Index $\geq 50^{\text{th}}$ percentile).^{27,28} At the time of the grant application, 688 individuals met these criteria. We will recalculate eligibility at the start of the trial, since attribution changes over time, but we expect the total number of eligible individuals to be similar. This population will be randomized to the two arms of the trial (344 per arm).

At the start of the study, we will have the list of participants and will randomize them into two groups. (We will be requesting a waiver of informed consent and a waiver of HIPAA authorization, as described below in section 4.3, so there will be no recruitment per se.)

The first 3 months after randomization will serve as the period during which individuals will have “qualifying events” for receipt of care coordination services. In the usual care group, a qualifying event is discharge from a hospitalization. In the intervention group, a qualifying event is a “positive screening call” (indicating a perceived problem with care coordination), as described in Section 5.2 below. Direct referrals from physicians to care coordinators for assistance with particular patients will be allowed in both groups.

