Individuals with qualifying events in both groups will receive care coordination services, which will be consistent with the professional standards of the American Case Management Association and the Case Management Society of America.^{29,30} Usual care includes describing care coordination to the patient or proxy and inviting them to engage in care coordination; approximately 70-80% of people agree to engage. Each interaction with a patient or proxy (including declining care coordination) is documented in the electronic health record (EHR). Usual care coordination is broad and encompasses post-discharge medication reconciliation, inquiries about any symptoms post-discharge, a review of upcoming appointments, assistance with obtaining transportation, review of paid home care services, and any other needs that may arise, with the primary goal of preventing rehospitalization. Patients and proxies are given the care coordinator’s contact information and are invited to reach out with any questions or concerns. Care coordination in the intervention group will start narrowly, with the care coordinator seeking to understand the positive screening result (exactly what the patient or proxy thinks is not working well and why). The care coordinator will then seek to address the issue, documenting the process in the EHR. The care coordinators will be free to engage in broader care coordination activities (e.g., general medication reconciliation, reviewing upcoming appointments, arranging transportation, etc.) at their discretion.

The length and frequency of interactions between the patient or proxy and the care coordinator varies depending on the patient’s needs and the care coordinator’s discretion. Patients are followed for a minimum of 30 days and a maximum of 1 year, which is a typical duration for care coordination.³¹ Care coordination starts at the time of the qualifying event. Follow-up for ED visits and hospitalizations begins after the first 30 days of care coordination.

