5.2 Handling of Study Interventions

As above, the intervention consists of a novel method for assigning care coordinators to PLWD based on perceived need. Perceived need will be measured with a previously validated 7-minute telephone survey. This survey consists of 22 questions, has been previously administered to more than 7,000 adults ≥ 65 years old (with funding from [name] R01 HL135199), and is published.³⁴ This published paper, which includes the survey instrument as an appendix, is being provided to the IRB with this protocol. The survey includes 8 questions regarding perceptions of care coordination; the other questions relate to self-reported ambulatory utilization and self-reported preventable adverse events. The 8 questions on perceptions of care coordination include 6 questions from the previously validated Care Coordination Measure for the Consumer Assessment of Healthcare Providers and Systems (CAHPS) Medicare survey, which was previously tested on more than 300,000 Medicare beneficiaries³⁵ These 8 questions ask (using different wording) whether the respondent has experienced difficulty with care coordination over the past 6 months, and the responses are ultimately combined into a single indicator for the presence or absence of a self-reported problem with or "gap" in care coordination. Of the 7,568 respondents in the original administration (average age 77 years), 38% reported a gap in care coordination.³⁴

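### Is the power statement in Section 9.2 misleading because a rate ratio of 0.74 is larger than the plan's own risk and uptake figures suggest?

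*Combined protocol and SAP*

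**What the plan says.** Section 9.2 defines the primary outcome as the number of ED visits or hospitalizations per person-time alive. It takes a control mean of 1.99 events per person from preliminary data. The calculation uses Poisson regression "with a sample size of 688 PLWD and assuming 20% attrition", alpha 0.05 and intention-to-treat, and reports more than 90% power at a ratio of 0.74: "a reduced event rate of 1.47 or lower in the intervention group vs. 1.99 in the control group". The plan describes that difference as meaningful. It does not call it the expected effect and cites no source for it.

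Other sections give figures that bear on the likely effect:

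- Section 2.2, on more versus less fragmented care: "The magnitude of this association is a 31% increase in the risk of an ED visit" and, separately, "an 18% increase in the risk of a hospital admission".
- Section 5.2, on the earlier administration of the screening survey: "38% reported a gap in care coordination".
- Section 3, on people offered coordination under usual care: "approximately 70-80% of people agree to engage".

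Section 4.3 states that all eligible individuals will be included.

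**The concern.** If the intervention works by removing the harm that fragmentation causes, the 31% and 18% excess risks suggest an upper bound on its benefit. Complete removal in every participant would still give ratios weaker than 0.74. Intention-to-treat analysis then dilutes the effect, because people who screen negative or decline stay in the intervention arm. Usual-care participants also receive coordination after a discharge, which narrows the contrast further. The 20% attrition allowance reduces the number analysed but does nothing about this dilution.

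On that reading, the power is quoted for an effect the trial is unlikely to produce. A non-significant result could then be taken as evidence against need-based allocation, when the trial had little chance of detecting the effect its rationale implies.

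**Working it through.** **Inputs.** 344 per arm (Section 3); 20% attrition, control mean 1.99, ratio 0.74, alpha 0.05 (Section 9.2; two-sided assumed, as sidedness is not stated); excess risks 31% and 18% (Section 2.2); 38% with a gap (Section 5.2); 70-80% engagement (Section 3).

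**1. The plan's own figure.** Analysed per arm: 344 × 0.80 = 275.2. Expected events: 275.2 × 1.99 = 547.6 (control) and 547.6 × 0.74 = 405.3 (intervention).

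SE of the log ratio = √(1/547.6 + 1/405.3) = 0.0655. |ln 0.74| = 0.301. Power = Φ(0.301/0.0655 − 1.96) = Φ(2.64) = 99.6%.

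The claim of more than 90% is reproduced with room to spare. Under the same model, power is 90% at a ratio of 0.81 and 80% at 0.84. If the variance is φ times the mean, the SE grows by √φ. Power at 0.74 stays at 90% up to φ of about 2.0 and is 76% at φ = 3. The documents give no variance, so these φ values are assumptions.

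**2. Full removal of the excess in everyone.** ED: 1/1.31 = 0.763, Poisson power 98.6%. Admission: 1/1.18 = 0.847, Poisson power 75%. Both ratios are weaker than 0.74. At the upper confidence limits (34% and 24%) they are 0.746 and 0.806.

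**3. Dilution, excess spread evenly.** Share reached = 0.38 × 0.70 to 0.38 × 0.80 = 0.266 to 0.304. Intention-to-treat ratio = 1 − reach × (1 − ratio in recipients).

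**4. Dilution, excess confined to people with gaps.** If the excess arises through coordination gaps and the survey finds those people, screening loses none of it. Only refusal dilutes: ratio = 1 − engagement × (1 − full-removal ratio). For ED at 80% engagement, 1 − 0.80 × 0.237 = 0.811.

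| Assumption | Outcome | Ratio | Poisson power | Power at φ = 2 |
|---|---|---|---|---|
| Spread evenly | ED | 0.93-0.94 | 18-23% | 11-14% |
| Spread evenly | Admission | 0.95-0.96 | 10-12% | 7-8% |
| In people with gaps | ED | 0.81-0.83 | 82-91% | 52-64% |
| In people with gaps | Admission | 0.88-0.89 | 44-55% | 25-31% |

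**5. Effect needed in recipients.** With even spread and average event rates, a ratio of 0.74 overall needs a fall of 0.26/0.304 = 86% to 0.26/0.266 = 98% in recipients' events. If recipients have twice the event rate of others (an assumption), they account for 42-47% of events, and the fall needed is 56-62%.

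Steps 3 to 5 assume no effect in people not reached and make no deduction for coordination in the usual-care arm.

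**The case for a change.** The strongest case for a change is that no assumption about reach recovers 0.74 from the plan's risk figures. Even 100% reach with complete removal stops at 0.763 for ED visits, and 0.746 at the upper confidence limit. The comparator is active, which pulls the ratio towards 1. Section 9.2 cites nothing in support of 0.74, and the remedy would cost one paragraph.

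Part of this stands. The choice of 0.74 is unexplained, and Section 9.2 makes no allowance for people who screen negative or decline. Taken at face value, the background figures do point to a weaker effect.

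What does not stand is treating those figures as limits:

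- The 31% and 18% are associations with a first event in the following 1-3 months among Medicare beneficiaries. The trial counts all events over 12 months in people with dementia, whom Section 2.1 regards as possibly more vulnerable to fragmentation.
- Section 2.2 makes the benefit conditional on the risk being modifiable and sets no ceiling. Coordinators may also reconcile medications, review appointments and arrange transport (Section 3), so benefit need not come only from the fragmentation excess.
- The 38% comes from older adults generally, not from people with dementia selected for fragmented care. The 70-80% is engagement under usual care, not among people who have just reported a problem.
- Reach has other routes: physician referral, contact details for people who screen negative, a further survey after any discharge, and record review when severe dementia leaves no proxy to call (Sections 4.3 and 5.2).
- The lowest powers, 10-23%, require the excess to be equally large in people with and without gaps. That fits poorly with a conceptual model in which harm arises through failures of communication.

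**Conclusion.** No change to the plan is needed. Section 9.2 states a power that the design has under its stated model: 99.6% at a ratio of 0.74, with 90% power down to about 0.81. There is no arithmetic error, and 0.74 is presented as a difference worth detecting, not as a forecast.

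The background figures, used as a rough guide, suggest ratios of about 0.81 to 0.96 and Poisson power from about 91% to 10%. That width comes mainly from an assumption the documents cannot settle: whether the excess risk lies in people with coordination gaps or is spread evenly. Overdispersion would lower every one of these powers, but it is a separate question about the variance model.

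How large an effect to power for is a judgement on which statisticians differ. Here it does not drive the size of the trial, since every eligible person is included. A fuller justification would read better, but it would leave the sample size, analysis, estimate and conduct as they are. The confidence interval for the rate ratio will show which effects the data exclude, and receipt of coordination is already among the planned implementation measures (Sections 5.4 and 9.4.2). The conclusion assumes a two-sided test and 20% attrition in each arm.

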9.2.1 Treatment Assignment Procedures

Randomization will be overseen by [name] (biostatistician). He will work with the data analyst at NYQC to enumerate the study population and conduct stratified randomization by care management team. That is, the study population will first be stratified into groups based on care management team. Within each group the study population will be randomized to the two trial arms, so that the trial arms will be of equal size. One rationale for randomizing by care management team is that the demographic characteristics of patients vary with care management team (for example, dual eligible beneficiaries are currently more likely to be assigned to one care management team than another). A second rationale for randomizing by care management team is that the clinical styles of care management teams may vary. By stratifying randomization by care management team, we will minimize any unmeasured confounding that variation by care management team might have otherwise introduced. Randomization will be done with random number generators.

Masking is not feasible for this study, so NYQC will be aware of which patients are allocated to which group. This is necessary, because they will need to conduct screening surveys for everyone in the intervention group.

9.3 Interim analyses and Stopping Rules

No interim analysis is planned, as the planned trial is fairly short, with 12 months of follow-up for the combined outcome of an emergency department visit or hospital admission. Interim analyses of emergency department visits and hospital admissions will not likely be sufficiently powered to be meaningful.

However, findings that might trigger a safety review are the number of unexpected deaths in the trial. Such findings are presented to the study statistician or to the Data and Safety Monitoring Board (DSMB) statistician to review the events by group to determine whether there are statistical as well as clinical concerns. The statistician reports his findings to a closed session of the DSMB or to the Safety Officer and/or NIA. The findings are used to determine what steps will be taken.

9.4 Outcomes

9.4.1 Primary outcome

We will measure the occurrence of ED visits and hospital admissions using Medicare claims.

